6.2 DATA SHARING PLANS

6.2.1 Human Data Sharing Plan

What data will be shared?

I will share human data generated in this research for future research as follows:

- Coded, linked data in an NIH-funded or approved public repository.
- Coded, linked data in BTRIS (automatic for activities in the Clinical Center)
- Coded, linked or identified data with approved outside collaborators under appropriate agreements.

How and where will the data be shared?

Data will be shared through:

- An NIH-funded or approved public repository: clinicaltrials.gov.
- BTRIS (automatic for activities in the Clinical Center)
- Approved outside collaborators under appropriate individual agreements.
- Publication and/or public presentations.

When will the data be shared?

- Before publication.
- At the time of publication or shortly thereafter.

6.3 RESPONSE CRITERIA

For the purposes of this study, patients should be re-evaluated for response every 8 weeks. In addition to a baseline scan, confirmatory scans should also be obtained 4-8 (not less than 4) weeks following initial documentation of objective response.

Response and progression will be evaluated in this study using the new international criteria proposed by the revised Response Evaluation Criteria in Solid Tumors (RECIST) guideline (version 1.1)[[40](#)]. Changes in the largest diameter (unidimensional measurement) of the tumor lesions and the shortest diameter in the case of malignant lymph nodes are used in the RECIST criteria.

6.3.1 Definitions

Evaluable for toxicity: All patients who signed consent will be evaluable.

Evaluable for objective response: Only those patients who have measurable disease present at baseline, have received at least one cycle of therapy, and have had their disease re-evaluated will be considered evaluable for response. These patients will have their response classified according to the definitions stated below. (Note: Patients who exhibit objective disease progression prior to the end of cycle 1 will also be considered evaluable.)

Evaluable Non-Target Disease Response: Patients who have lesions present at baseline that are evaluable but do not meet the definitions of measurable disease, have received at least one cycle of therapy, and have had their disease re-evaluated will be considered evaluable for non-target

disease. The response assessment is based on the presence, absence, or unequivocal progression of the lesions.

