2.2 SCREENING EVALUATION

2.2.1 Screening activities performed prior to obtaining informed consent

Minimal risk pre-screening activities that may be performed before the subject has signed a consent for this study include the following:

- Email, written, in person or telephone communications with prospective subjects
- Review of existing medical records to include H&P, laboratory studies, etc.
- Review of existing MRI, x-ray, or CT images
- Review of existing photographs or videos
- Review of existing pathology specimens/reports from a specimen obtained for diagnostic purposes

A waiver of consent for these activities has been requested in section [12.6.1](#).

2.2.2 Screening activities performed after a consent for screening has been signed (Registration Part 1)

The following activities will be performed only after the subject has signed the consent for this study for screening. Assessments performed at outside facilities or on another NIH protocol within the timeframes below may also be used to determine eligibility once a patient has signed the consent. For baseline evaluations, please see section [2.5](#).

Screening Assessments – Part 1

The following screening activities to determine eligibility may be performed any time prior to Registration Part 2.

Medical history, including age, performance status, and dates of prior treatment regimens.

Confirmation of tumor histology in NCI Laboratory of Pathology

(Archival tumor samples will be requested; if unavailable, the subject may choose to undergo fresh biopsy)

Assessment of disease by physical exam and imaging

Screening Assessments – Part 1

The following screening activities to determine eligibility may be performed any time prior to Registration Part 2.

(may include CT chest, abdomen and pelvis or MRI; report from outside institution is acceptable).

Screening Assessments – Part 2

Once patient eligibility has been established according to the results of the Screening Assessments Part 1 above, the following Screening Part 2 activities will be performed to determine final patient eligibility prior to Registration Part 2. Scans and x-rays must be done within 28 days (- 7 days) prior to the initiation of study therapy. All other studies should be performed within 7 days prior to initiation of study therapy, unless otherwise specified.

Assessment	Timeframe (calendar days)
	Within 7 days prior to treatment (unless otherwise noted)
History and physical examination	X

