Assessment of disease by imaging (may include CT chest, abdomen and pelvis)	Within 28 days prior to treatment
Ophthalmic evaluation including visual acuity and funduscopic examination performed by an ophthalmologist	Within 180 days (-14 days) prior to treatment
Assessment of venous access in Department of Transfusion Medicine	Anytime prior to apheresis
Intraperitoneal catheter placement in Interventional Radiology, if not already placed OR surgical implantation of intraperitoneal port by Gynecologic Oncology if not already placed OR verification by clinicians of functional IP catheter or IP port (if pre-existing)	X
CBC with differential and platelet count	X
Metabolic panel (magnesium, calcium, albumin, phosphorus)	X
Acute care panel (electrolytes, glucose, BUN, creatinine)	X

Assessment	Timeframe (calendar days)
	Within 7 days prior to treatment (unless otherwise noted)
Hepatic function tests (AST/ALT/total bilirubin)	X
CA125	X
β-HCG in women of childbearing potential	X

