2.3.1 Screen Failures

Screen failures are defined as participants who consent to participate in the clinical trial but are not subsequently assigned to the study intervention or entered in the study. A minimal set of screen failure information is required to ensure transparent reporting of screen failure participants, to meet the Consolidated Standards of Reporting Trials (CONSORT) publishing requirements and to respond to queries from regulatory authorities. Minimal information includes demography, screen failure details, eligibility criteria, and any serious adverse event (SAE).

Individuals who do not meet the criteria for participation in this trial (screen failure) may be rescreened at the discretion of the PI. Rescreened participants should be assigned a different participant number as for the initial screening.

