3 STUDY IMPLEMENTATION

3.1 STUDY DESIGN

This is a single arm dose escalation study including an expansion cohort at the MTD.

A 3+3 phase I trial of monocytes with Sylatron® (Peginterferon alfa-2b) and Actimmune® (Interferon gamma-1b) dose escalation will proceed to determine the MTD. The dose-limiting toxicity (DLT) period will be during the first cycle (28 days). For each dose level, three patients will be enrolled. There will be a 2 week wait from the time of cell infusion from one patient until apheresis and cell infusion of the next patient. If any patient assigned to a particular dose level experiences DLT, then up to three additional patients (up to a total of six patients) will be enrolled at that dose level. All patients on a dose-level must complete the 28-day cycle prior to beginning enrollment on the next dose level. If any patient experiences DLT-like adverse events related to experimental agents or study procedures in subsequent cycles, enrollment will be placed on hold until evaluated by the IRB and FDA.

Following Registration Part 2, patients will have intravenous access assessment in the Department of Transfusion Medicine (DTM) Dowling Clinic and a tunneled IP catheter will be placed in interventional radiology (IR) using ultrasound guidance. The tunneled IP catheter will be placed prior to start of the protocol therapy. If the patient already has an existing IP port for prior IP chemotherapy, this can be used for IP infusion, and a new tunneled catheter will not be placed. The patient will also be given the option to have an IP port placed instead of a tunneled catheter. If she prefers the IP port, she will be evaluated and if the procedure is deemed safe and feasible, it will be performed using direct visualization in the operating room (laparoscopic camera). Research blood will be collected, and ascites will be collected if present. In the expansion cohort, solid tumor will be biopsied if amenable at the time of catheter or port placement. The purpose of the biopsy is to assess monocyte and other immune cell infiltration and differentiation related to treatment.

On Day 0, the patient will undergo intravenous line placement and apheresis in DTM. PBMCs will be stored according to standard operating procedures of DTM ([Appendix B](#)). For patients on DL1 and DL3b, there will be no Day 0 in the calendar as they will not be apheresed.

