3.1.2 Dose Escalation

Patients who do not complete treatment in cycle 1 for reasons other than study drug-related toxicity will be replaced. If 1 of 3 patients experiences DLT, the dose level will be expanded to 6 patients. If 2 patients in a dose level of 3 to 6 patients experience DLT, then the MTD will have been exceeded and the next lower dose level will be expanded to 6 patients. MTD will be the highest dose at which 0-1 of 6 patients experience DLT. If the planned highest dose level is reached and determined to be safe after expansion to 6 patients, it will be considered the MTD. An expansion cohort of 10 additional patients will be treated at the MTD and the results combined with those of patients at the MTD to obtain improved estimates of safety and toxicity as well as to perform analyses to address secondary objectives. If either dose level 3 or dose level 4 exceeds the MTD (≥ 2 patients on either dose level experience a DLT) then we will enroll 3-6 patients on dose level 3b.

Total Volume (250 mL)

Dose Level	Monocytes total number	SYLATRON ® Peginterferon alfa2b, mcg (final concentration)	ACTIMMUNE ® Interferon gamma-1b, mcg (final concentration)
1	0	25 mcg (0.1 μ g/mL)	5 mcg (0.02 μ g/mL)

2	$75 \times 10^6 \pm 20\%$	25 mcg (0.1 $\mu\text{g}/\text{mL}$)	5 mcg (0.02 $\mu\text{g}/\text{mL}$)
3	$750 \times 10^6 \pm 20\%$	25 mcg (0.1 $\mu\text{g}/\text{mL}$)	5 mcg (0.02 $\mu\text{g}/\text{mL}$)
3b*	0	250 mcg (1 $\mu\text{g}/\text{mL}$)	50 mcg (0.2 $\mu\text{g}/\text{mL}$)
4	$750 \times 10^6 \pm 20\%$	250 mcg (1 $\mu\text{g}/\text{mL}$)	50 mcg (0.2 $\mu\text{g}/\text{mL}$)

*DL3b will enroll if ≥ 2 subjects enrolled on DL3 or DL4 experience DLT

Number of Patients with DLT at a Given Dose Level	Escalation Decision Rule
0 out of 3	Enter up to 3 patients at the next dose level
≥ 2	Dose escalation will be stopped. This dose level will be declared the maximally administered dose (highest dose administered). Up to three (3) additional patients will be entered at the next lowest dose level if only 3 patients were treated previously at that dose.

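### AE documentation opens at Day 0 (6.1), so non-serious harm from an earlier catheter placement or expansion biopsy need not be recorded; the 6.3.1 toxicity set also does not match the planned safety estimate

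*Combined protocol and SAP*

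**What the plan says.** **Start of AE capture.** Section 6.1 ties documentation to the first study intervention and, in the same sentence, identifies this as Study Day 0. Section 8.2 sends the reader to 6.1 for the recording period. The Adverse Events row of the 3.4 calendar is blank at Screening/Baseline and has its first mark in the Day -2 or -1 column. For serious events, 8.2 requires sponsor reporting from first product administration (Day 1). Section 8.3 requires reporting within 24 hours of awareness and gives no start date, and 8.4 grants no waiver.

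**Invasive procedures before Day 0.** Section 2.2.2 says that "the following Screening Part 2 activities will be performed to determine final patient eligibility prior to Registration Part 2", and its list includes "Intraperitoneal catheter placement in Interventional Radiology, if not already placed", to be done within 7 days before treatment. Footnote 7 of 3.4 allows placement at any time before therapy. Section 3.1 gives a different order: "Following Registration Part 2, patients will have intravenous access assessment in the Department of Transfusion Medicine (DTM) Dowling Clinic and a tunneled IP catheter" to be placed in interventional radiology. On the biopsy, 3.1 says: "In the expansion cohort, solid tumor will be biopsied if amenable at the time of catheter or port placement". The calendar marks the first biopsy in the Day -2/-1 column, and 5.1.4 lists it at Day 1 with a 48-hour margin either side.

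**Toxicity set.** Section 6.3.1 says of toxicity: "All patients who signed consent will be evaluable". Section 2.3.1 defines screen failures as people who "consent to participate in the clinical trial but are not subsequently assigned to the study intervention or entered in the study", and among adverse events its minimum data for them cover only serious ones. Section 3.1.2 has the expansion patients treated at the MTD and "the results combined with those of patients at the MTD to obtain improved estimates of safety and toxicity". Section 10 puts that group at 16 patients and names no separate toxicity set.

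**The concern.** Two parts of the safety plan do not fit together. The first, and the more important, is when recording begins. Section 12.5.1 lists intestinal perforation, abdominal fluid collection and death as risks of catheter or port placement, and pain, swelling, bleeding and infection as risks of biopsy. Section 3.1 treats harm from study procedures in later cycles as serious enough to put enrollment on hold. Yet the governing sentence on AE documentation can open after the first such procedures are over. A bleed or local infection that starts and settles before Day 0, in a patient who goes on to be treated, need not appear in the trial's safety data.

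The second is who counts as evaluable for toxicity. The consent-based wording admits people who never received any product and from whom no non-serious events are required. If anyone used that set as a denominator for regimen toxicity, it would include people who could not contribute a treatment-related event.

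**Working it through.** The point rests on no stated sample size or power figure, so the check sets the rules side by side and counts days.

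**Inputs.** Infusion is on Day 1 and apheresis on Day 0 (3.1). I take treatment in the 7-day rule of 2.2.2 to mean the Day 1 infusion, so the earliest placement under that rule is Day 1 - 7 = Day -6. Column positions are as I read the 3.4 table.

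**Days between procedure and opening of each window (DL4):**

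| Rule | Opens | Placement on Day -6 | Biopsy on Day -2 | Biopsy on Day -1 |
|---|---|---|---|---|
| 3.4, Adverse Events row | Day -2 or -1 | 4 to 5 | 0, if assessed at the same visit | 0, if assessed at the same visit |
| 6.1 | Day 0 | 0 - (-6) = 6 | 2 | 1 |
| 8.2, SAEs only | Day 1 | 1 - (-6) = 7 | 3 | 2 |
| 8.3, SAEs only | no start limit | 0 | 0 | 0 |

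Footnote 7 sets no earliest day for placement, so the placement gap under 3.4 and 6.1 has no stated upper bound.

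**Can the biopsy precede Day 0?** Yes, under each of the three passages. Section 3.1 takes it at placement, and the calendar puts it on Day -2 or -1. Section 5.1.4 allows Day 1 plus or minus 48 hours, which reaches back to 1 - 2 = Day -1. A Day -1 biopsy therefore satisfies both 3.4 and 5.1.4; a Day -2 biopsy lies outside 5.1.4.

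**Can the words first study intervention in 6.1 be stretched to cover placement?** Not on the text, because the same sentence fixes that point as Day 0. DL1 and DL3b have no Day 0 at all (3.1; 3.4 footnote 5), so there the 6.1 start is undefined. The expansion level, DL4, has one.

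**Exposure to the biopsy gap.** The expansion cohort has 10 patients. Section 5.1.3 requests a biopsy from all of them but obtains it only where feasible, and 12.5.1.8 and 12.6 call biopsies optional. Ten is therefore a ceiling.

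**Toxicity set.** Consent precedes screening (2.2.2), screen failures have consented (2.3.1), and 6.3.1 sets no dosing condition for toxicity although its next definition sets one for response. Never-dosed screen failures are thus inside the set as written. The planned safety estimate at the MTD uses 6 + 10 = 16 treated patients (3.1.2, section 10). A rate on the consent-based set would equal the treated-patient rate times treated / (treated + undosed), but the documents give no number of undosed patients. The accrual margin of 40 - 34 = 6 is an allowance for inevaluable patients and is not stated to count screen failures.

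**The case against.** Several points on the other side are sound.

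- *The calendar shows when an assessment is made, and 6.1 decides what is documented, so there is no conflict.* This is a fair reading of a schedule mark, which may be only a baseline check. It weakens the claim of a contradiction but leaves 6.1 alone in force, with its gap of 6 days for a Day -6 placement and 1 to 2 days for the biopsy.
- *Serious events are covered.* This stands. A reader might infer from the Day 1 start in 8.2 that earlier SAEs go unreported. The documents do not support that: 8.3 has no start limit, 8.4 waives nothing, 8.2 does not forbid earlier reports, 2.3.1 keeps SAEs for screen failures, and 3.3.4 and 7.3 address deaths. Sections 8.2 and 8.3 are inconsistent in wording, with no loss shown.
- *No specified analysis uses the 6.3.1 set.* This also stands. A reader might infer diluted toxicity rates or a doubtful MTD. Escalation counts patients per dose level with replacement (3.1.2), and the planned safety estimate uses treated patients. Any dilution percentage would need an assumed screen-failure share applied to a summary the plan does not describe.
- *A consent-based set is the one that could hold procedure harm.* True in principle, but 2.3.1 and 6.1 do not require the non-serious events that would fill it.
- *Exposure is limited.* Existing catheters or ports are used where present, biopsies are optional, and a complication still present at the Day -2/-1 examination may be noticed. If the order in 3.1 governs placement, screen failures with a catheter largely disappear. The gap in patients who are later treated remains.

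**Conclusion.** The point holds in a limited form and should be corrected. Section 6.1 leaves non-serious harm from catheter or port placement, or from the first expansion biopsy, outside required recording when onset is before Day 0. A complication of a catheter placed earlier in screening, for example on Day -6, can start and resolve before either the 3.4 or the 6.1 window opens. The number of events involved is unknown.

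The toxicity-set wording in 6.3.1 is a real but secondary mismatch with 3.1.2 and section 10. It changes no DLT decision, nor the declared MTD, nor the planned safety estimate at the MTD.

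The conclusion assumes that Day 1 is the start of treatment for the 7-day rule and that the calendar columns are as read above. If treatment were taken to start at Day 0 apheresis, the earliest placement under 2.2.2 would be Day -7 and each finite placement gap in the table would grow by one day.

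**What to change.** 1. Align 3.4, 6.1, 8.2 and 8.3 on one AE and SAE start, no later than the first study-specific invasive procedure after consent.
2. In 2.3.1, keep procedure-related adverse events, including non-serious ones, for screen failures who had such a procedure.
3. In 6.3.1, define the regimen-toxicity set as patients who received any study product, reported by dose level. Tabulate procedure-related events separately, with those who had the procedure as the denominator.
4. Reconcile 2.2.2 with 3.1 on whether placement comes before or after Registration Part 2, and 3.1, 3.4 and 5.1.4 on the day of the first biopsy. Which timing is right is for the investigators to decide.

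The cost is wording in six sections (2.3.1, 3.4, 6.1, 6.3.1, 8.2 and 8.3), plus a line each on placement and biopsy timing. Expect a few more AE records and possibly slightly higher reported toxicity. Sample size and dose-escalation results do not change.

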On Day 1, monocytes will be elutriated, quantified, and mixed with interferons. The final product will be infused in the inpatient setting through the IP catheter/port, as per standard operating procedure described in [Appendix D](#). Patient will be observed overnight for adverse events.

Patient will be discharged on Day 2, if well, with IV lines removed. IP catheter can be left in place or removed at physician discretion. Cycle will be repeated every 28 days. A new product will be manufactured for each treatment cycle.

In the expansion cohort, solid tumor will be biopsied again, if amenable, on C2D1 and at the time of disease progression. The purpose of these biopsies is to assess monocyte and other immune cell infiltration and differentiation related to treatment.

After 2 cycles, the patient may be treated as an outpatient per physician discretion.

Imaging will be performed at baseline and every 2 cycles.

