⁵ Day 0 procedures do not apply for patients in the Dose Level 1 or Dose Level 3b cohort ⁶Ophthalmic evaluation including visual acuity and funduscopy by an ophthalmologist within 180 days (-14 days) prior to treatment.

⁷ IP catheter or port can be placed at any time prior to the start of protocol therapy. If patient has pre-existing IP catheter or IP port, this will be assessed by the clinician for determination of function within the same time frame as other baseline studies. See Section 3.1 for additional information.

⁸ Research blood, ascites and biopsy testing will be performed in the NIH laboratory, [name]. [contact].

⁹ Restaging should be performed within +/- 7 days of completion of previous cycle.

¹⁰ As indicated in section 12.3, all subjects \geq age 18 will be offered the opportunity to complete an NIH advanced directives form. This should be done preferably at baseline but can be done at any time during the study as long as the capacity to do so is retained. The completion of the form is strongly recommended, but is not required.

¹¹ CA125 lab will be drawn at the beginning of each cycle. Day 2 labs will include only CBC with differential and platelet count, unless other labs are clinically indicated.

¹² Day 2 activities apply to the first two cycles only.

¹³ Apheresis collection will be done every 1-3 months provided there is an adequate monocyte population at the time of apheresis collection. If the apheresis collection is inadequate, apheresis can be done as frequently as each cycle to obtain the desired number of monocytes.

¹⁴ Do not repeat labs if already done within 1 week.

¹⁵ Performance score (ECOG) will be performed at the beginning of each cycle.

¹⁶ MRI is performed only as clinically indicated if patient cannot tolerate CT scan with IV contrast.

¹⁷ Screening and Baseline activities will be performed according to Sections [2.2](#) and [2.5](#) respectively.

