3.5.1 Criteria for removal from protocol therapy

- Progressive disease
- Participant requests to be withdrawn from active therapy
- Unacceptable Toxicity as defined in Section [3.1](#)
- Investigator discretion
- Positive pregnancy test
- Procedure failure (incapacity to do apheresis or obtain intraperitoneal access)
- Lost to follow-up
- Intercurrent illness

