10 STATISTICAL CONSIDERATIONS

Patients will be accrued in standard 3+3 dose escalation design, with expansion to 6 patients at the MTD and 10 additional patients at the MTD to allow for sufficient patients to perform correlative studies.

The 16 patients treated at the MTD (6 from dose escalation /MTD determination plus 10 additional patients) will be used to evaluate biologic correlates. With 16 patients, there would be 80% power to detect a change (either actual change or fold/relative change as appropriate) in the number of activated monocytes from baseline to after one cycle of treatment which would be equal to $\frac{3}{4}$ of a standard deviation of the difference measured (effect size 0.75) with a two-tailed 0.05 significance level paired t-test. If there are usable paired results from 10 patients instead of 16, this would result in the ability to detect a change with a 1.0 effect size based on the same parameters. In addition, a large number of other parameters will be obtained via flow cytometry and the changes from baseline to after one cycle of therapy will be determined. Given the large number of possible tests performed and the exploratory nature of the evaluation, there will not be any formal adjustment for multiple comparisons for these parameters. However, with 16 patients, there would be 80% power for any of the tests comparing baseline to post-treatment to detect a one SD difference between the two time points (effect size 1.0) with a two-tailed 0.01 significance level paired t-test; if there are 10 patients, there would be 80% power to detect a 1.0 effect size with a two-tailed 0.05 significance level paired t-test. The results of these exploratory tests will be reported in the context of the number of such tests performed.

The clinical response rate (in patients with measurable disease) and time to progression (in all patients) will also be estimated in a preliminary fashion. Appropriate confidence intervals will be provided along with fractions responding and a Kaplan-Meier curve of TTP.

It is estimated that up to 24 patients will be required to complete all 4 dose levels plus 10 additional patients will be needed at the MTD. Thus up to 34 evaluable patients may be required.

In order to allow for a small number of invaluable patients, the accrual ceiling will be set at 40 patients. Expected accrual rate is 1-2 patients per month. The DLT period is one cycle.

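### The response-rate denominator is unsettled: Section 6.3.1 drops measurable-disease patients who are never re-evaluated, Section 10 does not, and dropping any of them can only raise a non-zero rate

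*Combined protocol and SAP*

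**What the plan says.** Two sections of the protocol define the population for the response rate.

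- **Section 6.3.1 (Definitions)** restricts the response set to this group: "Only those patients who have measurable disease present at baseline, have received at least one cycle of therapy, and have had their disease re-evaluated". A note gives the one exception: "Patients who exhibit objective disease progression prior to the end of cycle 1 will also be considered evaluable".
- **Section 10 (Statistical Considerations)** begins its sentence on the analysis with "The clinical response rate (in patients with measurable disease", closes the bracket there, and goes on to "time to progression (in all patients) will also be estimated in a preliminary fashion". It sets no condition on cycles received or re-evaluation and does not point to 6.3.1. It promises fractions responding with confidence intervals.

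On timing, Section 3.1 states "Imaging will be performed at baseline and every 2 cycles" and Section 6.3 states "patients should be re-evaluated for response every 8 weeks". Footnote 9 of the Study Calendar (Section 3.4) adds "Restaging should be performed within +/- 7 days of completion of previous cycle".

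Section 1.1.2 makes response rate a secondary objective, and the précis gives better quantification of it as a purpose of the expansion cohort.

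**The concern.** Under 6.3.1, being in the denominator depends on something that happens after treatment starts, namely having a disease re-evaluation. Patients who stop early without one are unlikely to be a random subset, and none of them can be recorded as a responder. Leaving them out therefore moves the rate in one direction only.

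Section 10 read literally keeps these patients in but assigns them no outcome. Read as shorthand for 6.3.1, it removes them. The plan does not say which applies, so the choice could be made after the data are seen. Response and time to progression would also rest on sets that differ by more than measurable disease, which is the only distinction Section 10 draws.

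What is at stake is the reported response rate and its interval. The primary objective (the MTD), the sample size and the power statements are unaffected.

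**Working it through.** **The plan's own figure.** The documents give no target, assumed or expected response rate, so there is nothing to reproduce for this endpoint. The relevant counts are 16 patients at the MTD (6 + 10) and up to 34 evaluable patients overall (24 + 10), both from Section 10. Section 3.1.2 says the expansion patients are combined with the others at the MTD for the secondary objectives. Section 2.1.1.2 admits patients with evaluable but not measurable disease, so the number with measurable disease may be lower than either count.

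**Can a treated patient go unassessed?**

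1. A cycle is 28 days and imaging is every 2 cycles, so the first scheduled scan is at 2 × 28 = day 56, or days 49 to 63 with the 7-day window.
2. The 6.3.1 exception ends with cycle 1 (day 28). No response scan is scheduled by then, so using the exception requires an unscheduled scan or a finding on clinical examination.
3. Exits before the first scan are listed in Section 3.5.1 (toxicity, patient request, intercurrent illness, "Procedure failure (incapacity to do apheresis or obtain intraperitoneal access") and Section 3.5.2 (including death and starting another therapy). Table 3 in Section 3.3.3 also removes patients from treatment for certain severe events during the DLT period.
4. Section 6.3.4.3 provides a label for clinical decline without objective progression and asks that progression be documented later. The label alone does not bring a never-re-evaluated patient into the 6.3.1 set.

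**Formula.** Let N be the treated patients with measurable disease, k those never re-evaluated, and x the responders. An unassessed patient cannot be a documented responder, so x is the same on both denominators:

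- all measurable-disease patients: x/N
- 6.3.1 set: x/(N−k)
- ratio for x ≥ 1: [x/(N−k)] / [x/N] = N/(N−k)

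**Illustrations.** N, k and x are assumed, because the documents supply none of them. Intervals are Clopper-Pearson 95%.

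| N | x | k | x/N | x/(N−k) | Shift (points) | Ratio |
|---|---|---|---|---|---|---|
| 16 | 2 | 1 | 2/16 = 12.5% (1.6–38.3) | 2/15 = 13.3% (1.7–40.5) | 0.8 | 1.07 |
| 16 | 2 | 2 | 2/16 = 12.5% (1.6–38.3) | 2/14 = 14.3% (1.8–42.8) | 1.8 | 1.14 |
| 16 | 2 | 3 | 2/16 = 12.5% (1.6–38.3) | 2/13 = 15.4% (1.9–45.4) | 2.9 | 1.23 |
| 16 | 3 | 3 | 3/16 = 18.8% (4.0–45.6) | 3/13 = 23.1% (5.0–53.8) | 4.3 | 1.23 |
| 12 | 2 | 3 | 2/12 = 16.7% (2.1–48.4) | 2/9 = 22.2% (2.8–60.0) | 5.6 | 1.33 |
| 16 | 0 | 3 | 0/16 = 0% (upper limit 20.6) | 0/13 = 0% (upper limit 24.7) | 0 | n/a |

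If all dose levels were pooled at N=34, the ratio would be 34/33 = 1.03 for k=1 and 34/31 = 1.10 for k=3.

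**The case against.** The strongest reply is that there is no conflict. Section 6.3.1 is worded exclusively, and the bracket in Section 10 may only be contrasting measurable disease with the all-patient set used for time to progression. Section 10 also plans in terms of evaluable patients. On that reading 6.3.1 governs, the rule was disclosed in advance, and the criticism is a preference for a stricter convention. That reading is reasonable, and the two sections are not a flat contradiction. But it leaves the problem in place, because the governing rule then conditions the denominator on a post-treatment event that removes only patients who cannot be responders.

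A second reply is that k may be small. Removal from therapy does not end follow-up, and Section 3.5 asks for a safety visit about 30 days after the last dose. The restaging row of the Study Calendar, whose table is broken in the text available, may include a post-therapy scan. Patients with documented progression in cycle 1 stay in the set. All of this stands and would reduce k, and if k is 0 nothing changes. It does not guarantee k = 0: death, refusal, loss to follow-up or a new therapy can still come before any scan, and footnote 2 of the calendar allows telephone follow-up once another regimen or palliative care has begun.

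A third reply is that the effect is slight. The estimate is preliminary and has no test or decision rule. At N=16 with 2 responders, the largest shift shown is 2.9 points against an interval about 37 points wide (38.3 − 1.6 = 36.7). This also stands. It limits the importance of the point but does not justify an undefined denominator.

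**Conclusion.** The concern holds. The plan does not settle the denominator for a secondary endpoint, and the narrower of its two definitions is biased upward whenever at least one measurable-disease patient is never re-evaluated and at least one patient responds. The direction and the factor N/(N−k) are exact under those two conditions.

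The size depends on assumed counts: 0.8 to 2.9 percentage points for N=16, 2 responders and k=1 to 3, and 5.6 points for N=12, 2 responders and k=3. With no responders, only the upper confidence limit moves. This should be corrected, but its effect is confined to the reported rate and interval.

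**What to change.** State one rule in both Section 6.3.1 and Section 10:

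- **Main response rate:** all treated patients with measurable disease at baseline, with anyone lacking a post-baseline disease assessment counted as a non-responder.
- **Reporting:** the number never re-evaluated, with reasons.
- **Sensitivity analysis:** the current 6.3.1 evaluable set, labelled as such.

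The cost is wording in two sections. No new visits, data or patients are needed. The reported rate may be a few points lower, and the convention is conservative for patients who stopped for reasons unrelated to their disease. Reporting the sensitivity analysis and the reasons for missing assessments lets a reader judge that.
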